5.2.2.3. Secondary Endpoints

- Proportion of study eyes with ≥7 dB improvement from baseline at ≥5 of 16 central loci of the 10-2 grid assessed by MAIA microperimetry at 1, 2, 3, 6, and 9 months
- Change from baseline in retinal sensitivity at the central 16 loci assessed by MAIA microperimetry at 1, 2, 3, 6, 9, and 12 months
- Proportion of study eyes with ≥7 dB improvement from baseline at ≥5 of 68 loci of the 10-2 grid assessed by MAIA microperimetry at 1, 2, 3, 6, 9, and 12 months
- Change from baseline in retinal sensitivity at 68 loci assessed by MAIA microperimetry at 1, 2, 3, 6, 9, and 12 months

- Change from baseline in BCVA at 1, 2, 3, 6, 9, and 12 months
- Change from baseline in visual field assessed by Octopus 900 perimeter at, 3, 6, and 12 months

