8.6. Study Masking

Part I of the study is open label.

Part II is double-masked (subject, surgeon, investigator/site team, and sponsor will be masked) to the assigned dose, and open-label with respect to the treatment procedure.

In Part II, ophthalmic assessments that will be used as efficacy endpoints (BCVA, LLVA, microperimetry, contrast sensitivity will be conducted by appropriately qualified assessors (see Table 1). For the immediate post-operative visits, masking of the assessors will not be viable as clinical signs of surgery will be apparent (i.e., redness, swelling). Therefore, unmasked assessors will perform all ophthalmic assessments at Visit 3 (Day 1), Visit 4 (Day 7), Visit 5 (Month 1), and Visit 5.9 (Month 2). From Visit 6 (Month 3) onwards, masked assessors will be used, as signs of surgery will have dissipated and it should not be possible clinically to differentiate between those subjects that have not undergone surgery, and those subjects that have undergone surgery and received active treatment. It is preferable that the same assessor who performed the efficacy endpoint assessments at Screening/Baseline also perform the assessments during the masked period from Month 3 to Month 12.

Table 1 Masked Assessments of Efficacy

Masked Assessments at Month 3, 6, 9 and 12 Post-Treatment with AAV8-RPGR

- Best-corrected visual acuity
- > Low-luminance visual acuity
- Microperimetry
- Contrast sensitivity

>

Subjects randomised to the untreated Control group will not be required to attend the site at Visit 2, 3 or 4. As the key purpose of Visit 2 is surgery, and Visit 3 and 4 are post-operative safety visits, there is limited utility in Control subjects attending. Therefore, to limit the study burden for Control subjects thereby potentially reducing the risk of subject withdrawal at this stage and reducing the possibility of further unmasking due to direct contact and communication with fellow participants, Control subjects are not scheduled to attend the clinic for study visits at these times.

To minimise bias further, masked assessors will not have access to the subject's medical records, source documentation or eCRF as data entries or notation (such as use of peri-

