9.13. Early Termination (ET) Visit

If a subject discontinues the study at any time, the site should use every reasonable effort to ensure that an ET Visit is conducted. The following assessments should be performed:

- Collection of safety blood samples (hematology and clinical chemistry)
- Full ophthalmic examination, including indirect ophthalmoscopy, a slit-lamp examination, IOP, anterior chamber and vitreous inflammation grading and LOCS III cataract grading
- LLVA¹
- ETDRS BCVA¹
- SD-OCT
- Fundus autofluorescence
- MAIA microperimetry¹
- Octopus 900 visual fields²
- Fundus photography
- Contrast sensitivity test¹
- •
- Immunogenicity sampling
- AE/SAE monitoring
- 1,4
- Review of concomitant medication, treatments, and procedures
 - 1. In Part II, at the ET Visit, LLVA, BCVA, microperimetry, contrast sensitivity, and the will be conducted by qualified masked assessors.
 - 2. Octopus 900 perimetry is specified for visual field assessments only in Part II.
 - 3. In Part II and only at sites with available technology.

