The proportion of eyes with improved retinal sensitivity, for both the center grid and the whole grid, at Month 12 will be compared between study arms (high dose vs untreated; low dose vs untreated) using the Fisher's Exact-Boschloo test with a Berger-Boos correction of beta=0.001 (Berger 1994). The difference in proportions between treatment groups will be presented with its corresponding 80% CI calculated using the method of Miettinen and Nurminen (Miettinen 1985).

• Primary Endpoint:

The intercurrent event is discontinuation of study early or lost to follow-up for this study. The estimand is the response rate difference between treatment and control group in ITT Analysis Set regardless of intercurrent events. The treatment policy strategy will be used for the intercurrent events. Observed data collected within 6 months outside the last visit window will be included in the analysis, including data collected after intercurrent events [ICH E9(R1) addendum 2019], i.e. discontinuation of study early or lost to follow-up.

For other missing data due to intercurrent events or other reasons, the following missing data imputation methods will be provided.

Primary analysis for missing data imputation:

The last observation carried forward method (LOCF) will be applied to the underlying continuous variables of retinal sensitivity. The imputed value will then be dichotomized based on the responder criteria, i.e., improvement of \geq 7 dB from baseline. Imputation of retinal sensitivity will be done at locus level, i.e. if a locus value is missing at a visit, the last non-missing value will be carried over to this visit.

This is a hypothetical strategy based on the assumption that the retinal sensitivity of subjects who are discontinued from the study early or lost to follow up will remain unchanged from the last observed value until the month-12 visit. This is considered a plausible assumption due to 1) the slow progression of the disease for the untreated eyes, and 2) the durability of efficacy demonstrated for the treated eyes for up to 18 months based on the current Part I data.

In addition to the primary analysis, 2 supplementary analyses are proposed under different assumptions for the estimand to assess efficacy in subjects who have missing data.

Supplementary analysis for missing data imputation:

Supplementary Analysis I:

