The composite strategy will be used for the intercurrent event. The non-responder imputation method will be applied on locus level. i.e. if a locus value is missing at a visit, it will be imputed as a failure. This is a conservative approach in that any missing data will be considered as a non-responder.

Supplementary Analysis II:

The hypothetical strategy will be used with the assumption that the retinal sensitivity of the subjects who have discontinued the study early or lost to follow-up will be similar to those subjects who remain in the study. The multiple imputation approach will be applied to the missing data on the locus level under the assumption of missing-at-random (MAR). MAR assumption is considered plausible since treatment is only administered once for gene therapy after randomization in the study. Subjects do not take ongoing doses after surgery. Subjects who are lost to follow up or drop out early are not related to the effect of ongoing dose taken. These missing data are regarded missing at random. The missing retinal sensitivity data at each locus will be imputed by the method of multiple imputation. Each imputed data set will be analyzed using two-sample Binomial test. The analyzed results from the imputed dataset will be combined based on Rubin's rule (Rubin 1987) for inference assuming the statistics estimated from each imputed dataset are normally distributed.

Sensitivity analysis

It was identified that microperimetry data from one site were impacted by a protocol deviation involving assessments conducted by an unmasked rather than masked assessor from month 3 to month 12. Microperimetry is an automated test that measures the minimum luminance of a light stimulus that can be perceived by a subject at defined locus of the retina. The impact of an unmasked assessor on results is limited due to the automated nature of the test, in that the assessor is not directly involved in generating or recording the results. In addition, the perceived light stimulus at a specific locus is tested by projecting multiple stimulus points of varying light intensities. The projection strategies further reduce the probability of an unmasked assessor significantly impact the data. However, an unmasked assessor can still introduce bias into the results in indirect ways, e.g., by encouraging the subject to stay focused during the test. The risk of significantly altering microperimetry results by an unmasked assessor is believed low.

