Although the risk is low, to mitigate this risk a sensitivity analysis will be implemented by excluding mean sensitivity data assessed by unmasked assessor at Part II, Month 12. The sensitivity analysis will be applied to the summaries for the proportion of eyes with mean sensitivity ≥ 7 db improvement from baseline at ≥ 5 of the 16 loci at Month 12. The sensitivity analyses will be descriptive only and analyzed on observed case. For microperimetry data in Part II, the main analysis is still based on ITT analysis set. The

sensitivity analysis will be compared with the main analysis to assess the robustness of the data.

Exploratory analysis

Secondary Endpoint:

The secondary endpoint is the change from baseline in mean sensitivity of the 16 central loci and 68 whole loci at 1, 2, 3, 6, 9 and 12 months. Observed data collected within 6 months outside the last visit window will be used regardless of intercurrent events, i.e. discontinuation of study early or lost to follow up. Observed value and change from baseline will be summarized by treatment groups, visits and eyes. The CI for observed value will be provided based on one-sample t-test, and the CI for change from baseline will be provided by paired t-test. The difference of change from baseline between treatment and control group at each visit will be provided. The CI and p-value for the difference will be also provided, which are calculated based on two sample t-test.

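### Should the carry-forward rule for the Month 12 primary endpoint exclude the unmasked Month 1 and Month 2 microperimetry exams?

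*SAP*

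**What the plan says.** SAP 7.12.1 and 7.12.2 make last observation carried forward (LOCF), applied at each locus, the primary way of handling missing data for the Month 12 responder endpoint: "if a locus value is missing at a visit, the last non-missing value will be carried over to this visit". No earliest visit, masking status or maximum gap is given for the exam that supplies the value.

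Microperimetry is done before masking begins. Protocol 5.2.2.3 has the 16-locus responder outcome on the 10-2 "grid assessed by MAIA microperimetry at 1, 2, 3, 6, and 9 months". Protocol 8.6 states that "unmasked assessors will perform all ophthalmic assessments at Visit 3 (Day 1), Visit 4 (Day 7), Visit 5 (Month 1), and Visit 5.9" (Month 2). SAP 6.5 names only Days 1 and 7 as unmasked, but it too starts masked assessment at Month 3.

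Three other provisions bear on the point:

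- Early termination, Protocol 9.13: "In Part II, at the ET Visit, LLVA, BCVA, microperimetry, contrast sensitivity, and the will be conducted by qualified masked assessors". The gap after the word 'the' is a redaction.
- Supplementary Analysis I in SAP 7.12.2 scores a missing locus as a failure: "This is a conservative approach in that any missing data will be considered as a non-responder".
- SAP 7.6 requires the number, pattern and timing of missing data to be examined, with the reasons.

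On assessor influence, SAP 7.12.2 says "The risk of significantly altering microperimetry results by an unmasked assessor is believed low", while accepting that "an unmasked assessor can still introduce bias into the results in indirect ways". Its analysis of the one-site masking deviation excludes unmasked Month 12 data, and "The sensitivity analyses will be descriptive only and analyzed on observed case".

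**The concern.** The trial masks assessors at baseline and from Month 3 to protect the comparison with untreated controls. A carry-forward rule with no donor condition lets an exam from the unmasked window stand in for the Month 12 result in the only formally tested primary comparison. The SAP defends LOCF by slow progression in untreated eyes and durability in treated eyes. Neither argument concerns how the donor exam was masked.

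With about ten eyes per arm, one eye can move the result across a significance boundary. The planned masking sensitivity analysis would not show this, because it carries nothing forward and repeats no test.

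**Working it through.** **1. When the rule matters.** All of these must hold for a locus:

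- a Month 1 or Month 2 value exists;
- there is no value at Months 3, 6, 9 or 12, with Month 12 accepted up to 6 months outside its window (SAP 7.3, 7.12.2);
- there is no usable masked early termination exam. The SAP does not say whether such exams can be donors.

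If baseline were the only value and were carried forward, the change would be 0 dB and the locus would not count as improved. The documents give no count of eyes meeting these conditions; it may be zero.

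**2. Reproduce the plan's figure.** Inputs from SAP 6.6: 10 treated and 9 control eyes, 50% versus 5%, one-sided 0.10, Fisher's Exact-Boschloo test with Berger-Boos 0.001. For each of the 11 × 10 = 110 possible tables, the one-sided Fisher p-value is the ordering statistic. Its tail probability is maximised over the 99.9% Clopper-Pearson interval for the common rate, and 0.001 is added. Power is the sum of Bin(10, 0.5) × Bin(9, 0.05) over tables with p at or below the level.

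- Level 0.10: 86.8% (SAP: about 87%).
- Level 0.05, the second Hochberg step in SAP 7.5: 71.9%.

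**3. How far one eye can move the test.**

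| Control responders | Treated responders | p |
|---|---|---|
| 0/9 | 3/10 | 0.063 |
| 0/9 | 2/10 | 0.179 |
| 1/9 | 4/10 | 0.096 |
| 1/9 | 3/10 | 0.195 |

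**4. Error under the current rule, by assumption.** Suppose the true Month 12 rate is 5% in both arms, and one or two treated eyes are classed on an early exam with a 25% to 50% chance of response. Rejection at 0.10 rises from 0.8% to 1.6%–2.6% with one eye and 3.1%–7.7% with two. All stay below 0.10.

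**5. Cost of barring early donors.** Take the obvious rule: without an exam from Month 3 on, the locus keeps its baseline value and the eye is a fixed non-responder, with group sizes unchanged. For one treated eye, Bin(10, 0.5) becomes Bin(9, 0.5); for one control eye, Bin(9, 0.05) becomes Bin(8, 0.05).

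| Affected eyes | Power at 0.10 | Power at 0.05 |
|---|---|---|
| none | 86.8% | 71.9% |
| one treated | 81.3% | 62.5% |
| two treated | 73.9% | 51.2% |
| one control | 87.9% | 73.3% |

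Per-comparison false-positive rate at 0.10, before and after one control eye is fixed as a failure:

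| Common true rate | None | One control eye |
|---|---|---|
| 5% | 0.76% | 0.79% |
| 20% | 8.2% | 9.7% |
| 30% | 9.5% | 12.2% |

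**6. Compare with what is already planned.** For an eye with no locus value after Month 2, Supplementary Analysis I scores all 16 loci as failures. The donor rule sets all 16 changes to 0 dB. Both make the eye a non-responder.

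**7. Timing.** The Version 11 amendment summary gives the last enrolment as 30 September 2019. Allowing the full 12 weeks to Visit 2 gives 23 December 2019; adding 12 months and 14 days gives 6 January 2021. The same summary says study drug expired at the end of September 2019. If the last treated eye was dosed by then, its Month 12 window closed about 14 October 2020. Both dates precede SAP Version 4.0 (10 March 2021).

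**The case for a change.** The strongest case for a change is that the omission is real and touches the primary test. No passage restricts the donor, and the SAP itself treats unmasked Month 12 data at one site as a major deviation. Supplementary Analysis I is not a clean substitute: it also fails loci that have valid masked values at Months 3 to 9, so it does not isolate the effect of early donors. A donor rule would take two sentences, would alter nothing if no eye is affected, and would settle the choice before results are known.

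The omission stands, and so does the point that Supplementary Analysis I is broader than needed. The remedy does not follow. Masking is not a condition of entry to the primary analysis: SAP 7.12.2 keeps the deviating site's unmasked Month 12 exams in the main intent-to-treat analysis. Barring Month 1 and 2 donors while admitting known unmasked later exams would apply the principle selectively. A masked donor would also remove assessor influence only, since subjects know throughout whether they had surgery. And the rule would discard observed post-treatment data in favour of a return to baseline, for which the documents offer no support, whereas the SAP gives reasons for assuming stability.

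**Conclusion.** The plan can stand. The missing donor condition is a narrow gap in wording. It matters only for an eye seen at Month 1 or 2 and then lost without a usable masked exam, and no such eye is documented. The size and direction of any masking bias cannot be derived from the documents.

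Restricting donors would be a trade-off with no demonstrated gain. It costs 5.5 points of power for one affected treated eye (86.8% − 81.3%, at 0.10). An affected control eye could take the per-comparison error above 0.10 at a 30% common rate, far from the planned 5% control rate. These figures assume 10 versus 9 eyes and an affected eye scored as a certain failure.

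Supplementary Analysis I already shows the result with such an eye as a non-responder. The review of missing-data timing under SAP 7.6 lets analysts count by arm any eye classed on a Month 1 or 2 exam. What remains is a preference about which analysis is called primary, and in-window Month 12 visits were probably complete before SAP Version 4.0. The silence of SAP 6.5 on Months 1 and 2 is clerical: Protocol 8.6 settles their status, and both documents start masking at Month 3.

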10. ASSESSMENT OF EFFICACY

All efforts should be made to conduct the efficacy assessments; if a subject is not able to perform an assessment due to poor VA, it will be documented accordingly in the eCRF and will not be recorded as a protocol deviation.

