within each group and the 80% CI for proportion will be calculated by the Clopper-Pearson method. For BCVA gain from baseline ≥ 10 and ≥ 15 letters, where subjects are expected to show more pronounced improvement in treated eyes than non-treated eyes, the difference in proportion between the treatment group and control group will be presented with its corresponding 80% CI calculated using the method of Miettinen and Nurminen (Ref. Miettinen and Nurminen, 1985), and the p-value will be reported by the Fisher's Exact-Boschloo test with a Berger-Boos correction of beta=0.001(Berger 1994). In the event of missing BCVA data, the primary analysis to analyse the proportion of study eyes with BCVA gain or maitenenace from baseline is LOCF approach.

To account for BCVA data from one site impacted by a protocol deviation involving assessments conducted by an unmasked rather than masked assessor from month 3 to month 12, a sensitivity analysis will be conducted evaluating safety signals for BCVA loss from baseline. A summary table of BCVA loss from baseline $\geq 5, \geq 10, \geq 15$ letters will be summarized at each visit, by excluding BCVA data impacted by unmasking.

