7.13 Safety Analysis

Safety analysis will be performed using the Safety Analysis Set. All safety analyses will be summarized based on observed case.

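### A test not done because vision is too poor is handled as ordinary missing data, so an eye that responded and then became untestable stays a responder in the primary analysis

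*SAP*

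**What the plan says.** Protocol section 10 states that "if a subject is not able to perform an assessment due to poor VA, it will be documented accordingly in the eCRF" and that this is not a protocol deviation. Section 11 repeats the rule for safety assessments. Neither section assigns a score or an outcome.

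SAP 7.6 undertakes to look at the amount, pattern, timing and reasons of missing data. SAP 7.12.2 then defines the event of interest narrowly: "The intercurrent event is discontinuation of study early or lost to follow-up for this study". Everything else is swept into the same methods: "For other missing data due to intercurrent events or other reasons, the following missing data imputation methods will be provided". For the primary endpoint the method is locus-level LOCF: "if a locus value is missing at a visit, the last non-missing value will be carried over to this visit". The stated grounds are "the slow progression of the disease for the untreated eyes" and, for treated eyes, durability of effect seen in Part I. Supplementary Analysis I scores missing loci as failures. Supplementary Analysis II uses multiple imputation, because "These missing data are regarded missing at random".

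For acuity, SAP 7.12.3 states that "the primary analysis to analyse the proportion of study eyes with BCVA gain or maitenenace from baseline is LOCF approach", and 7.12.4 does the same for LLVA. On safety, SAP 7.13 states: "All safety analyses will be summarized based on observed case".

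**The concern.** When an eye cannot be tested because it sees too poorly, the reason for the missing value is closely tied to the outcome being measured. LOCF replaces that value with one from before the loss. Missing-at-random methods replace it with what the eye's earlier results and the still-testable eyes would predict. An observed-case table leaves it out. Each of these gives a better result than the recorded reason suggests, or no result.

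The stakes come from the sample size. There are about 10 eyes per arm, the LOCF analysis decides success, and the study is declared positive if either dose succeeds. Treated study eyes undergo vitrectomy and retinal detachment, and protocol 6.3 lists visual impairment among the risks, so a severe loss in a treated eye is a foreseeable event.

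**Working it through.** **1. Follow one eye through the SAP.** Suppose a Part II study eye attends Month 12 but the tests are not performed because of poor vision.

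| Output | Rule | Result for this eye |
|---|---|---|
| Primary responder (7.12.2) | LOCF by locus | Keeps its status from the last tested visit |
| Supplementary Analysis I | Missing locus = failure | Non-responder |
| Supplementary Analysis II; mean sensitivity (7.12.2) | Multiple imputation under MAR | Predicted from its earlier values and from testable eyes |
| BCVA/LLVA change (7.12.3, 7.12.4) | MMRM under MAR | No value; modelled implicitly as above |
| BCVA/LLVA gain, maintenance (7.12.3, 7.12.4) | LOCF | Keeps its last status |
| BCVA/LLVA letter loss (7.13.2, 7.13.3) | Observed case | Absent from that visit |

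**2. Do the justifications fit?** The LOCF argument is that sensitivity stays unchanged in subjects who leave the study. An eye recorded as too poor to test has changed. The MAR argument is that a single administration makes dropout unrelated to continued dosing. That concerns leaving the study, not losing the ability to be tested.

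**3. Reproduce the stated power.** Inputs from SAP 6.6: 10 treated v 9 untreated, 50% v 5%, one-sided 0.10, Boschloo test with Berger-Boos 0.001. For a table (a, b), let F be the one-sided Fisher p-value and C the 99.9% Clopper-Pearson interval for the common rate π given a+b of 19. Then

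p(a,b) = max over π in C of Σ Bin(i;10,π)·Bin(j;9,π) over all (i,j) with F(i,j) ≤ F(a,b), plus 0.001.

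Exact enumeration gives power of 86.8%, against the stated 87%. The plan's figure is reproduced.

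**4. Rescore one carried-forward responder as a failure.** One-sided p-values from the same enumeration:

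| Treated responders | v 0/9 | v 1/9 |
|---|---|---|
| 5/10 | 0.011 | 0.043 |
| 4/10 | 0.027 | 0.096 |
| 3/10 | 0.063 | 0.195 |

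Under SAP 7.5 (Hochberg) both doses succeed if the larger p is below 0.10; otherwise the smaller must be below 0.05. Losing one responder crosses 0.05 from 4/10 to 3/10 v 0/9 and from 5/10 to 4/10 v 1/9. It does not from 5/10 to 4/10 v 0/9. A second eye against 1/9 (3/10, p=0.195) also crosses 0.10.

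**5. Effect on power at one-sided 0.10.** If one of 10 treated eyes must count as a failure and the rest respond at 50%, power is 81.3%. With two such eyes it is 73.9%.

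**6. Letter-loss table.** Part II entry requires at least 34 letters (protocol 7.2.1), so an eye that can read none has lost at least 34 − 0 = 34. With no other losses, observed case shows 0/9 = 0% instead of 1/10 = 10%, or 0/8 = 0% instead of 2/10 = 20% for two eyes.

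**7. Mean sensitivity.** The entry range for mean total sensitivity is 0.1 to 8 dB, and MAIA scores an unseen locus as −1. A whole grid at the floor is a change of −1 − 0.1 = −1.1 dB to −1 − 8 = −9 dB. In a 10-eye arm, one such eye moves the mean by −0.11 to −0.90 dB compared with imputing no change. The central 16 loci have no entry range, so this bound is for the whole grid only.

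**The case against.** Several points on the other side stand.

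- **The SAP does look at reasons.** SAP 7.6 examines them, and protocol 12.2 says handling will depend on the nature and frequency of missing data. A reader might infer that the reason is ignored altogether. The documents support less: it is examined but does not determine the imputation.
- **Completed tests already score poor vision.** An unseen locus is −1, and acuity is a count of letters with a 1-metre fallback, so zero letters can be recorded. The gap concerns tests not performed. The documents do not show how sites would code those.
- **The loss is not hidden from safety reporting.** Protocol 11.2.1.2 makes major vision loss an SAE, and SAP 7.13.1 has dedicated tables of reduced-acuity events. What is missing is the eye's entry in the by-visit letter-loss tables.
- **The bias need not favour treatment in every comparison.** It is tempting to infer that it does, because only treated eyes have surgery. But XLRP is progressive, and untreated eyes can become untestable too. Scoring those at the floor would widen a difference in means.
- **LOCF creates a false responder only from an eye that had already responded.** Supplementary Analysis I gives the adverse reading, so a reader will see both. It is supplementary, however, does not decide success, and covers only the responder endpoint.
- **Poor vision does not show that all 68 loci are unseen.** It may also be temporary. The documents therefore do not support −1 dB everywhere and zero letters as the main analysis values.

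**Conclusion.** The gap is real and limited. As written, a test not performed because of poor vision goes to LOCF or MAR methods whose justifications address dropout, or drops out of the letter-loss tables. An eye that responded and later became untestable counts as a responder in the analysis that decides the trial.

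The size is conditional. No document gives a rate of untestable Part II eyes; one treated eye is an assumption. With one eye, the conclusion for a dose changes in two of the three one-responder changes considered in the working, and only if the other dose fails the 0.10 step. Both p=0.063 and p=0.096 still succeed if the other dose is also below 0.10. In the letter-loss tables, one eye is 10 percentage points of a 10-eye arm. If no such eye occurs, nothing changes.

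The stated power is correct for its assumptions, and a reader should not infer otherwise. The fault lies in the missing-data rule.

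**What to change.** Amend SAP 7.12.2 to 7.12.4 and 7.13.2 to 7.13.3 before the final analysis. Name an assessment not performed because of poor vision as an intercurrent event, in treated and untreated arms alike, with a composite strategy at the visit concerned:

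- **Microperimetry responder:** non-responder in the primary analysis.
- **BCVA and LLVA categories:** not gained and not maintained.
- **Letter-loss tables:** counted as a loss of at least 15 letters. Entry sets no LLVA minimum, so for LLVA this is a worst-case convention; flag any eye whose baseline is below 15 letters.
- **Mean sensitivity and BCVA/LLVA change:** keep the planned analysis and add a sensitivity analysis at the floor (−1 dB per locus, 0 letters).
- **Reporting:** tabulate such eyes by arm and visit.

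Keep the existing rules for all other missing data.

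The cost is a short SAP amendment and a little programming, after confirming that the reason can be extracted from the eCRF; the protocol says only that it is documented. Responder and safety results for an affected arm can become slightly less favourable, with the loss of power shown in the working.

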10.4. MAIA Microperimetry

MAIA Microperimetry will be conducted for both eyes at the times indicated in Table 3, Section 16.1. MAIA microperimetry will be conducted by certified technicians to assess changes in retinal sensitivity within the macula. Microperimetry must be performed on both eyes in triplicate and should be conducted over a 2-day period at Visit 1 for all subjects. The final assessment should be used to determine subject eligibility. If at subsequent visits there are obvious technical challenges or the subject is not performing the assessment as expected from previous visits (e.g. distracted, large number of false positive responses, not maintaining fixation, etc), then the assessment may be repeated and the second assessment should be used for that study visit.

All microperimetry images will be sent by the sites to a CRC for review. For complete technical specifications for microperimetry, refer to the Study Operations Manual (which will include procedures from the CRC regarding how measurements are to be taken).

In Part II, it is preferable that the same masked assessor who performs the microperimetry assessments during the masked period from Month 3 through Month 12 also perform these assessments at screening.

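### The check on the unmasked Month 12 microperimetry exams is descriptive and observed-case only, so as pre-specified it does not show whether the success decision stands without them

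*SAP*

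**What the plan says.** **The deviation.** SAP 7.12.2 reports that microperimetry at one site involved "assessments conducted by an unmasked rather than masked assessor from month 3 to month 12". SAP 7.14 classes the affected Month 12 data as major protocol deviations because Month 12 is the primary-analysis visit. SAP 7.12.2 judges the risk low because the test is automated and "the assessor is not directly involved in generating or recording the results". It also accepts that an unmasked assessor may bias results indirectly.

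**The check.** SAP 7.12.2 repeats the Month 12 responder summaries "excluding mean sensitivity data assessed by unmasked assessor at Part II, Month 12". Of these summaries it says: "The sensitivity analyses will be descriptive only and analyzed on observed case". Their stated purpose is that the "sensitivity analysis will be compared with the main analysis to assess the robustness of the data".

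**The primary analysis.**
- Missing data, SAP 7.12.2: "The last observation carried forward method (LOCF) will be applied to the underlying continuous variables of retinal sensitivity". This is done locus by locus, and the result is then dichotomised.
- Test, SAP 7.12.2: each dose against untreated by Boschloo with Berger-Boos 0.001, with an 80% Miettinen-Nurminen interval for the difference.
- Decision, SAP 7.5 (multiplicity): Hochberg at one-sided 0.10. If the larger p-value is 0.10 or more, the smaller must be below 0.05. Either dose suffices for a positive study.

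The two supplementary analyses in SAP 7.12.2 (non-responder and multiple imputation) deal with missing data only. They do not remove the unmasked exams.

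**The concern.** The check is the plan's only response to a self-declared major deviation in the primary endpoint, and it stops short of the quantity on which the trial is judged. It produces responder proportions by arm. The decision rests on an exact p-value passed through two Hochberg thresholds. Neither document specifies a test, a between-arm interval, a Hochberg step or a robustness criterion for the reduced data. The Clopper-Pearson interval that SAP 7.12.2 allows is within-arm.

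There is a second, conditional difficulty. The main analysis uses LOCF and the check uses observed cases. If any other subject lacks Month 12 data, comparing the two changes the missing-data rule as well as the exams used, and the two effects are mixed.

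At stake is whether a reader of the final report can tell, from something fixed in advance, that the claim of success does not depend on the unmasked exams.

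**Working it through.** **Inputs.** SAP 6.6: 10 treated v 9 untreated, response rates 50% v 5%, one-sided 0.10, stated power about 87%. SAP 7.5: thresholds 0.10 and 0.05. Protocol synopsis: about 30 Part II subjects and about 7 centres. The number and arms of the affected eyes are not given.

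**Method.** All 2×2 tables were enumerated. Each table's one-sided Fisher p is the ordering statistic. The Boschloo p is the largest probability of a table at least as extreme, taken over the 99.9% Clopper-Pearson interval for the common rate, plus 0.001.

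**Step 1: reproduce the plan's power.** With 0, 1, 2 or 3 control responders out of 9, significance at 0.10 needs at least 3, 4, 6 or 7 treated responders out of 10.

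- Probability of 0, 1, 2, 3 control responders at 5%: 0.6302, 0.2985, 0.0629, 0.0077.
- Probability of at least 3, 4, 6, 7 treated responders at 50%: 0.9453, 0.8281, 0.3770, 0.1719.
- Power = 0.6302×0.9453 + 0.2985×0.8281 + 0.0629×0.3770 + 0.0077×0.1719 ≈ 0.868.

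This agrees with the stated 87%. At 0.05 the minimum counts are 4, 5, 7 and 8, and power is 71.9%.

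**Step 2: what exclusion can do to the decision.**

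| Before | p | Removed | After | p | Effect |
|---|---|---|---|---|---|
| 4/10 v 0/9 | 0.027 | one treated responder, one control non-responder | 3/9 v 0/8 | 0.076 | crosses 0.05 |
| 3/10 v 0/9 | 0.063 | same | 2/9 v 0/8 | 0.171 | crosses 0.10 |
| 5/10 v 0/9 | 0.011 | same | 4/9 v 0/8 | 0.027 | none |
| 4/10 v 0/9 | 0.027 | one treated non-responder, one control non-responder | 4/9 v 0/8 | 0.027 | none |
| 4/10 v 0/9 | 0.027 | one treated responder only | 3/9 v 0/9 | 0.0498 | none, narrowly |

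In the first row the descriptive table would show 40% becoming 33%. The Hochberg decision changes only if the other dose also has p≥0.10. If the other dose is below 0.10, a p-value of 0.076 still passes at the first step.

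**Step 3: the cost of exclusion in power.** Equal recruitment is an assumption. It gives 30/7 ≈ 4 subjects per centre, or 4/3 ≈ 1.4 per arm. The range below is 0 to 3 removed per arm.

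| Treated v control | Power at 0.10 | Power at 0.05 |
|---|---|---|
| 10 v 9 | 86.8% | 71.9% |
| 9 v 8 | 82.6% | 63.9% |
| 8 v 7 | 76.7% | 54.0% |
| 7 v 6 | 68.7% | 42.2% |

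A larger p-value after exclusion is therefore expected to some degree even if unmasking had no effect.

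**The case against.** **A like-for-like comparator exists.** Protocol 12.6 and SAP 7.12.1–7.12.2 already provide descriptive Part II summaries, on observed data under Protocol 12.6, and the exclusion is applied to those summaries. Observed-case proportions with and without the unmasked exams differ only by the exclusion. This stands. A reader might infer that no difference could ever be attributed to unmasking, and the documents do not support that. The mixing arises only against the LOCF main analysis, which the SAP names as its comparator, and only if other Month 12 data are missing. The documents do not say that any are.

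**Arm counts let anyone compute the p-value.** Also true, so it would be too strong to say that the table cannot reveal the answer. But that calculation would be post hoc, with no agreed rule.

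**Observed case has a sound reason.** The site was unmasked from Month 3, so LOCF would replace a removed Month 12 exam with an unmasked earlier one. This stands and shapes the fix.

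**A p-value that rises after exclusion is not evidence of bias.** Correct, as step 3 shows. It bears on how a rerun is read, not on whether to run one. The exact test remains valid at 9 v 8.

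**The risk is low.** Protocol 10.4 gives one route to indirect influence: if there are technical problems or the subject is not performing as expected, "then the assessment may be repeated and the second assessment should be used for that study visit". The text limits the grounds, does not say who decides, and sends the images to a central reading centre. It is context for the SAP's own concession about indirect bias, not a separate error.

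**Conclusion.** The point holds in a limited form. The pre-specified check does not show whether the Hochberg decision stands without the unmasked Month 12 exams. Its named comparator also uses a different missing-data rule, which matters if other Month 12 data are missing.

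The size is illustrative. At 10 v 9 the decision can turn on one or two eyes (0.027 to 0.076), but only in some tables and, at the 0.05 step, only when the other dose also has p≥0.10. At the planned 50% treated rate, with no control responders, the same removal does not flip it (0.011 to 0.027). The number and arms of the affected eyes are unknown, and about four per centre assumes equal recruitment.

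A reader might go further and infer that the primary claim is unsound or that unmasking biased it. The documents show neither. They show a disclosed deviation whose check is weaker than it needs to be.

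One editorial slip: the SAP describes the endpoint as "the proportion of eyes with mean sensitivity ≥ 7 db improvement from baseline at ≥ 5 of the 16 loci at Month 12", with similar wording in 7.14, whereas SAP 5.2.2.1 and the definitions in 7.12.2 apply the 7 dB criterion at individual loci. The locus count makes the meaning clear, so this needs a wording correction only.

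**What to change.** Keep the descriptive table and add one pre-specified rerun of the primary analysis:

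- Exclude, from all arms, subjects whose Month 12 exam was unmasked. Report the number excluded by arm.
- Label it a sensitivity analysis in a subset of the ITT set.
- Use the same locus-level responder definition and, for the remaining subjects, the primary missing-data rule, but do not carry forward any exam affected by the deviation. A subject whose Month 12 value could come only from such an exam should also be excluded and counted.
- Apply Boschloo with Berger-Boos 0.001, both Hochberg steps and the 80% Miettinen-Nurminen interval.
- Read the change in the estimated difference and its interval alongside the p-value, because exclusion alone lowers power (86.8% to 82.6% at 0.10 and 71.9% to 63.9% at 0.05, if one eye per arm is lost).
- Delete 'mean sensitivity' from the responder endpoint description in SAP 7.12.2 and 7.14.

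The cost is SAP wording and one rerun of existing code; the primary analysis is unchanged. The downside is that a larger sensitivity p-value may be put on record.
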